This material is the property of the Mayo Clinic. Do not disclose or use except as authorized.

A liver biopsy is required for confirmation of ASH for all patients with clinically-diagnosed AH who have one or more of the following possible confounding factors:

1. Possible ischemic hepatitis (e.g., severe upper gastrointestinal bleed, hypotension, or cocaine use within the prior 7 days)
2. Possible drug-induced liver injury/jaundice
3. Recent sepsis (i.e., infection requiring antibiotics within the prior 7 days)
4. Uncertain alcohol assessment (e.g., patient denies recent/excessive alcohol use)
5. Atypical laboratory tests (e.g., AST < 40 IU/mL or >500 IU/mL, AST/ALT ratio <1.5).

Alcoholic hepatitis usually persists and progresses to cirrhosis if heavy alcohol use continues. If alcohol use ceases, alcoholic hepatitis resolves slowly over weeks to months, sometimes without permanent sequelae but often with residual cirrhosis.

Corticosteroids have been utilized as a standard of care in various treatment guidelines for patients with severe alcoholic hepatitis, as manifested by hepatic encephalopathy or a Maddrey Discriminant Function > 32. However, their applicability in clinical practice is limited in “special populations” of patients who have contraindications to corticosteroids and/or fall into subcategories of patients who were not included in the corticosteroid treatment trials that formed the basis of these treatment guidelines. These special populations are substantial and include patients with renal failure, infection, GI bleed, pancreatitis, and viral hepatitis. Pentoxifylline has also been used because of its safety, but several well-conducted studies have not supported the efficacy of pentoxifylline for the treatment of severe AH. A recent study has questioned the efficacy of both prednisone and pentoxifylline in the treatment of alcoholic hepatitis. Mortality at 6 months was similar in patients on either prednisone, pentoxifylline, or both as compared with placebo. Therefore, there is a need for investigational therapies.

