We define response to the study drug as a decrease in the AST/ALT or serum triglycerides by 30% or more from baseline to Day 42 or Day 56. We will evaluate the patients' response rate for each cohort in phase I. If at the MTD level, the response rate is seen in only 1 of the 3 patients, an additional group of 6 patients will be recruited and treated at the MTD dose level. If efficacy signals can yet not be demonstrated in 2 or more of the 6 patients, the drug will be deemed ineffective. If efficacy signals are demonstrated at the highest safe dose, patients in the final cohort will be administered a third dose (10mcg/kg, 30 mcg/kg, or 45mcg/kg) of the MTD on Day 7 (± 3 days) following the second dose to determine if efficacy can be increased with additional dosing.

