2.2 Study Design/Type

Schedule of Procedures

Safety Assessments	Screening (-72 hrs)	Day 1 (± 1 day)	Day 3 (± 1 day)	Day 7 (± 3 days)	Day 14 (± 3 days)	Day 28 (± 4 days)	Day 42 (± 2 days)	Day 56 ⁶ (± 2 days)
Inclusion/Exclusion Criteria	X	X						
Physical Examination	X			X	X ⁵	X	X	X
Medical/Surgical History	X		X	X	X	X	X	X
Nutritional Assessment	X				X ⁵		X	X
AUDIT and NIAAA Questionnaires	X							
Timeline Followback Questionnaire	X					X	X	X
Vital Signs	X		X		X	X	X	X
Serial Vital Signs		X		X	X ⁵			
Serum Chemistry ^A	X	X	X	X	X	X	X	X
Coagulation ^A	X	X	X	X	X	X	X	X
Hematology ^A	X	X	X	X	X	X	X	X
Serum pregnancy test	X							
Urine pregnancy test		X		X	X ⁵			
Lipid profile, CRP, SAA1, total protein, albumin ^A	X			X	X ⁵	X		
Calculate MELD Score	X	X	X	X	X	X	X	X
Calculate Lille Score				X				
Calculate Maddrey Score	X							
Urinalysis ¹	X							
ECG ²	X			X	X ⁵	X		
Chest X-ray ³	X							
Adverse Events		X	X	X	X	X	X	X
Concomitant Medications	X	X	X	X	X	X	X	X
Study Drug Dosing		X		X	X ⁵			
Pharmacokinetic Sample Collection ⁷		X	X	X	X	X	X	
Immunogenicity Testing ⁸	X				X	X	X	
Biomarkers(blood and urine)	X ⁷			X	X	X	X	X
Confirmation that patient is abstinent from alcohol		X	X	X	X	X	X	X

1. Urinalysis results can be used for Screening if tested within 7 days.
2. ECG results can be used for Screening if tested within 7 days.
3. Chest X-ray results can be used for Screening if tested within 30 days.
4. Day 1, Day 7 and Day 14 labs and testing must be completed prior to dosing.
5. These tests/procedures will occur only on Day 14 if the patient is receiving a 3rd dose at that visit.
6. Day 56 will only occur if the patient received a 3rd dose on Day 14.
7. Biomarkers are optional at Screening.

^AClinical Laboratory Tests

Hematology	Coagulation	Serum Chemistry		Urinalysis	Other
		Liver Function Tests	Other Chemistry		
Complete Blood Count with differential, Platelet count, MCV	PT, INR	AST, ALT, Total Bilirubin, Direct Bilirubin	Sodium, Potassium, Chloride, Bicarbonate, Calcium, Magnesium, Phosphate, Creatinine, BUN, Glucose, Total protein, Albumin, Lipid profile, CRP, SAA1	Specific gravity, pH, Blood, Protein, Glucose, Ketones	β-HCG serum pregnancy test Urine pregnancy test

Blood will be collected for PK sampling per the schedule below:

⁸Pharmacokinetic Sampling Schedule

Study Visit Day					Study Visit Day +0*	Study Visit Day +2*	Study Visit Day +3*	Study Visit Day +4*
					24 hrs	48 hrs	72 hrs	96 hrs

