2.4 Trial Treatment

Participants will receive 10 µg/kg, 30 µg/kg or 45 µg/kg of F-652 on Day 1 and Day 7 via slow intravenous infusion. Three patients will receive 10 µg/kg of F-652.

Pharmacokinetic testing will be completed on these subjects. If evaluations demonstrate safety and efficacy signals, the next 3 patients will receive 30 µg/kg. If pharmacokinetic testing demonstrates safety and efficacy signals, the next 3 patients will receive 45 µg/kg. If evaluations demonstrate safety and efficacy signals, patients with a MELD score of 21-28 will receive a third dose of the study drug at the maximum tolerated dose on Day 14.

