5.2 Method and Timing

1. MELD score will be calculated at each visit.
2. Lille score will be calculated on Day 7.

CONFIDENTIAL

This material is the property of the Mayo Clinic. Do not disclose or use except as authorized.

3. Triglycerides, CRP and SAA1 will be collected at Screening, Day 7, Day 14 (if dosed) and Day 28.
4. AST and ALT will be collected at Screening, Day 3, Day 7, Day 14, Day 28, Day 35, Day 42 and Day 56 (if applicable).
5. Adverse events will be evaluated at each study visit per the Schedule of Procedures by the study coordinator and reviewed by the investigator

6 *Assessment of Safety*

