7.1 Statistical Methods

Primary endpoint (safety): The number and percentage of patients with SAE and increase in MELD score > 5 up to Day 56 following administration of first dose of study drug will be summarized by each dose level. Ninety-five percent confidence interval of the percentage will be calculated too.

Summary of adverse event will also be provided by each dose level.

Secondary endpoint: Pharmacokinetics (PK) and pharmacodynamics (PD) of F-652 in patients with alcoholic hepatitis at the first dose level (10ug/kg) and subsequent dose levels will be determined by the study sponsor using standard pharmacological tools. The total exposure (area under the curve), maximum serum concentration, time at maximum concentration, last measurable serum concentration, time at last measurable concentration, clearance, volume of distribution, elimination half-life, accumulation ratio and dose proportionality will be calculated.

Efficacy signal endpoint: The main efficacy end point is the reduction of AST/ALT or serum triglycerides. If patients show a reduction of AST/ALT or serum triglyceride by 30% at day 42, the drug shows efficacy in this patient. We will calculate the percentage of patients with efficacy (rate) and its 95% confidence interval for each dose level.

We will also use the proportion of patients with 30% change of AST, ALT from baseline to Day 3, Day7, Day14, Day 28, Day 42 and Day 56 as the dependent variable, dose level and baseline AST, ALT and other patients' characteristic at baseline as the covariates to evaluate the change (efficacy) or drug by dose level. A random intercept will be included for accommodating the correlation among the repeated measurement.

Other efficacy endpoints: Paired t-test or signed-rank test will be used to compare the level Lille score. Linear mixed-effect models will be used to analyze the MELD score, triglycerides, CRP, and SAA1 in a similar way to the AST/ALT.

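### Section 7.1 states no visit term in the repeated-measures models, although Day 56 exists only for three-dose patients at the MTD; if a third dose is given and recovery continues without drug, the dose-level effect tilts towards the MTD

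*Combined protocol and SAP*

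**What the plan says.** The second efficacy paragraph of section 7.1 takes the proportion of patients whose AST/ALT changes by 30% "from baseline to Day 3, Day7, Day14, Day 28, Day 42 and Day 56 as the dependent variable, dose level and baseline AST, ALT", plus further baseline characteristics as covariates. On the repeated records it adds: "A random intercept will be included for accommodating the correlation among the repeated measurement". Visit or time does not appear in the list. The other markers follow the same pattern: "Linear mixed-effect models will be used to analyze the MELD score, triglycerides, CRP, and SAA1 in a similar way to the AST/ALT".

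The visits are not the same for everyone. A footnote to the Schedule of Procedures in section 2.2 says: "Day 56 will only occur if the patient received a 3rd dose on Day 14". Section 5.2 says: "Triglycerides, CRP and SAA1 will be collected at Screening, Day 7, Day 14 (if dosed) and Day 28".

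The third dose is tied to one dose level. Section 2.4 says that, if safety and efficacy signals are seen, "patients with a MELD score of 21-28 will receive a third dose of the study drug at the maximum tolerated dose on Day 14". The dose expansion text in section 1.6 says instead that, if efficacy signals are seen, "patients in the final cohort will be administered a third dose" of the MTD. On the untreated course, section 1.1 says: "If alcohol use ceases, alcoholic hepatitis resolves slowly over weeks to months".

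**The concern.** A model that stacks visits and has no visit term compares dose levels on their average over whatever visits each level happens to have. Here the extra late AST/ALT and MELD records all fall in the MTD level. If patients who stop drinking go on improving between Day 42 and Day 56, that improvement enters the dose-level coefficient. A random intercept does not prevent this. It allows for correlation within a patient, but not for a difference in visit timing between dose levels.

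At stake is the only planned covariate-adjusted comparison of AST/ALT across dose levels, in a trial with no control arm. Section 1.6 gives the third dose to learn whether more dosing increases efficacy, so the unequal visits lie along the comparison of interest. Section 2 also asks for improvement at Days 7, 28, 42 and 56, and a model without visit cannot give estimates by day.

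**Working it through.** The plan gives no figure for this model, so there is none to reproduce. (The 22 subjects in section 1.9 belong to the overall response rate and do not bear on this point.)

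**Inputs from the documents**
- AST/ALT visits in 7.1: Days 3, 7, 14, 28 and 42 for all patients; Day 56 for three-dose patients only. Section 5.2 also lists a Day 35 sample, but the schedule has no such visit and 7.1 does not use it.
- Triglycerides, CRP and SAA1 after screening: Days 7 and 28 for all; Day 14 only if dosed.
- Patients: 18, with two MELD strata of 3 per dose, so 6 per dose level (section 1.8).
- Untreated 30% response: 15-20% (section 1.9). The sentence is garbled and gives no day.

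**Assumptions**
- The 15-20% is reached at Day 42, and the drug does nothing.
- Time course: flat; linear, p(d) = p42 × d/42; or saturating, p(d) = p42 × (1 − e^(−d/14)) / (1 − e^(−3)).
- Three-dose share of the MTD level: 3 of 6 (for example, only its MELD 21-28 patients), or all of it as an upper bound.

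**Visit mix**
- Five visits: (3+7+14+28+42)/5 = mean day 18.8.
- Six visits: (3+7+14+28+42+56)/6 = mean day 25.0.
- Shift under a linear trend: 25.0 − 18.8 = 6.2 days of natural slope if all have three doses. A generalised least squares calculation of the random-intercept model gives the same 6.2 days, and about 3.1-3.2 days if 3 of 6 do.

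**Odds ratio with no drug effect, linear course, p42 = 20%**
- Two-dose pooled rate: 0.20 × 18.8/42 = 0.0895. Three-dose: 0.20 × 25.0/42 = 0.1190.
- All on three doses: (0.1190/0.8810) / (0.0895/0.9105) = 1.37.
- 3 of 6: pooled rate (15 × 0.0895 + 18 × 0.1190)/33 = 0.1056, odds ratio 1.20.

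| Course | p42 | 3 of 6 on three doses | All on three doses |
|---|---|---|---|
| Flat | 15% or 20% | 1.00 | 1.00 |
| Saturating | 15% | 1.06 | 1.12 |
| Saturating | 20% | 1.07 | 1.12 |
| Linear | 15% | 1.20 | 1.36 |
| Linear | 20% | 1.20 | 1.37 |

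**Check with a fitted model.** A large simulation of correlated binary data with no drug effect (linear course, 20% at Day 42) was fitted by logistic regression with exchangeable correlation. Without visit, the top-versus-bottom dose odds ratio was 1.19 (half) and 1.39 (all). With categorical visit it was 1.00 and 1.03, where the standard error of the log odds ratio was 0.04. With a flat course and no visit term it was 1.02 and 0.99.

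**Against sampling error.** Take a continuous outcome with a natural trend of 1 SD over 42 days and intraclass correlation 0.6 (both assumed). With 18 patients the shift is 0.07 SD (half) or 6.2/42 = 0.15 SD (all), against a standard error of about 0.47 SD. Two-sided type I error rises from 5% to about 5.3% or 6.1%.

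**Triglycerides, CRP, SAA1.** The extra Day 14 record moves a patient's average by (Day 14 mean − average of the Day 7 and Day 28 means)/3. For a linear trend this is (14 − 17.5)/3 = −1.2 days of slope. The documents give no untreated trend for these markers, so the shift could be zero. Under the same assumed trend, type I error is 5.0%.

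**The case against.** The strongest reply is that 7.1 is a summary. The Statistical Methodology entry of the Study Summary leaves detail to a separate analysis plan, which is not in the supplied text, so silence on visit is not a decision to omit it. The model is also supporting. The main efficacy rate is read at Day 42 alone, the primary endpoint is safety, escalation follows dose-limiting toxicity, and no stated decision rests on the model. The third dose is conditional too. Sections 1.6 (dose expansion), 2.4 and 4.3 tie it to efficacy signals, so under those passages an inert drug reaches Day 56 only through a false-positive signal.

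Most of this stands, and it sets the size of the point. It does not remove it: the covariates are listed, visit is not among them, and the model run as listed gives a worse answer than one with visit.

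The documents do not support some stronger readings that a reader might infer:
- That the dose effect must shift even if the drug does nothing. The design fixes only an unequal visit mix, and only once a third dose is given. With a flat course the shift is exactly zero.
- That CRP and SAA1 are made to look worse at the MTD. The CRP rise in section 1.5 follows dosing at 30 and 45 µg/kg, so it is a drug effect and not an untreated trend.
- That the odds ratio could be larger because half or more of untreated patients respond by Day 56. Section 1.9 puts untreated response at 15-20% and keeps 50% for treated patients.
- That early leavers seriously penalise a dose level. Sections 3.4, 3.5 and 6.9 ask withdrawn patients for Day 42 procedures or completed follow-up, which limits this.

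**Conclusion.** The point holds for AST/ALT and MELD, with two conditions: a third dose is actually given, and the outcome improves over time without drug. The second follows from section 1.1 in direction but not in size. For AST/ALT response, the spurious odds ratio favouring the MTD is about 1.1-1.2 if half of that level has three doses and about 1.1-1.4 if all of it does. This rests on placing the 15-20% of section 1.9 at Day 42 and on the assumed shape of the climb. No untreated MELD trend is given in figures, so only the direction can be stated there.

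For triglycerides, CRP and SAA1 the documents show an unequal visit mix across dose levels, and no more than that.

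The distortion is small beside the sampling error of 18 patients. It should still be corrected, because the correction is nearly free and the tilt favours the group whose extra dosing is under test.

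**What to change.** In section 7.1, or in the separate analysis plan:
1. Base dose-level contrasts on visits scheduled for every patient: Days 3, 7, 14, 28 and 42 for AST/ALT and MELD; Days 7 and 28 for triglycerides, CRP and SAA1.
2. Add visit as a fixed effect, categorical in the linear models. In the binary AST/ALT model, use continuous time, merged early visits or a penalised fit if early visits have few or no responders. Under the linear course with 20% at Day 42, the Day 3 rate is 0.20 × 3/42 = 1.4%, so 18 patients give 0.26 expected responders and a chance of 0.986^18, about 77%, of none. A categorical visit term would then often fail to converge. For the same reason, do not add dose-by-visit terms to the binary model.
3. Report Day 56, and the Day 14 markers taken only when dosed, descriptively for three-dose patients.
4. Reconcile the places that say who receives the third dose and on what condition: the Study Summary, section 1.6 (Phase II and dose expansion text), section 2.4 and section 4.3. The visit imbalance cannot be fixed in the analysis plan until they agree.

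The cost is wording, a few degrees of freedom for visit, and the loss of Day 56 from the dose contrast. No new data are needed.

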Objectives	
 a. Assess the safety and tolerability of F-652 in patients with alcoholic hepatitis as determined by absence of unexpected serious adverse events up to Day 42 or Day 56 following administration of first dose of study drug. b. Determine the pharmacokinetics (PK) and pharmacodynamics (PD) of F-652 in patients with alcoholic hepatitis. c. Assess the efficacy signals of F-652 in patients with alcoholic hepatitis (compared to historical patient data) as determined by : 
 A. Clinical: improvement in clinical status B. Biochemical: Improvement in liver biochemistry, MELD and Lille scores at days 7, 28, 42 and 56. C. Biomarkers of IL 22 activity (CRP, SAA, triglycerides),
Number of Subjects	Up to 18 participants at approximately six sites.

CONFIDENTIAL

This material is the property of the Mayo Clinic. Do not disclose or use except as authorized.

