Diagnosis and Main Inclusion Criteria	
Alcoholic hepatitis is a syndrome of progressive inflammatory liver injury associated with long-term heavy intake of ethanol. The pathogenesis is not completely understood⁷. Patients who are severely affected present with subacute onset of fever, hepatomegaly, leukocytosis, marked impairment of liver function (e.g., jaundice, coagulopathy), and manifestations of portal hypertension (e.g., ascites, hepatic encephalopathy, variceal hemorrhage). However, milder forms of alcoholic hepatitis often do not cause any symptoms.
 
To participate in this study, patients must meet all of the following criteria:
 
 1. Able to provide written informed consent (either from patient or patient's legally acceptable representative) 2. Male or female patients 21 years of age or older 3. Patients with alcoholic hepatitis defined as: 
 a. History of heavy alcohol abuse use: >40 g/day in females and >60 g/day in males for a minimum period of 6 months AND b. Consumed alcohol within 6 weeks of entry into the study AND c. Serum bilirubin > 3mg/dL AND AST >ALT, but less than 500 U/L d. MELD score between 11-28 e. Liver biopsy will be carried out to confirm diagnosis in all patients except those who meet criteria a-c and in whom other causes of liver disease have been excluded (viral, drug, autoimmune etc). 4. Women of child-bearing potential must utilize appropriate birth control. 
*Patients on steroids and/or pentoxifylline will not be excluded from the study.

Study Product, Dose, Route, Regimen	F-652 with a dose escalation regimen using 10 µg/kg, 30 µg/kg and 45 µg/kg.
Duration of Administration	Participants will be given a dose of F-652 on Day 1 and Day 7 of the study. Following demonstration of safety with the Day 1 and Day 7 dose in the patient group with MELD score 21-28, a 3rd dose of the maximum tolerated dose will be administered on Day 14
Reference therapy	There is not a standard reference therapy or placebo against which the study product is being compared.

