1.9 Power Calculation

As the primary outcome is observational, we have powered this study based upon the efficacy outcome, which is defined as a biochemical signal for success if AST/ALT is reduced by at least 30% on treatment. With no treatment, approximately 15-20% of patients reach this outcome following study drug treatment. We anticipate that a minimum of 50% will achieve this outcome. Using a conservative 2-sided assessment of superiority (50% with outcome vs. 20%), we will require 22 subjects to reach 80% statistical power.

For our efficacy outcome of AST/ALT, our primary analysis will assess a binary outcome of at least 30% reduction when on treatment. We will evaluate this with a 95% confidence interval of the percentage of subjects who have at least 30% reduction in AST/ALT on treatment, using an exact binary confidence interval. As a secondary analysis, we will use

CONFIDENTIAL

This material is the property of the Mayo Clinic. Do not disclose or use except as authorized.

robust linear regression with the change in AST/ALT at follow-up as compared to baseline as the outcome variable and baseline AST/ALT as the predictor. We will pair this analysis with a Bland-Altman plot. The goal of the secondary analysis is to assess the degree to which the reduction in AST/ALT attributable to treatment changes according to the subject's baseline AST/ALT. We will use 2-sides 5% type I error rate throughout.

2 *Study Objectives*

Primary:

- Assess the safety and tolerability and find the MTD of F-652 in patients with alcoholic hepatitis as determined by:
 - a. Absence of unexpected serious adverse events and,
 - b. Absence of worsening of alcoholic hepatitis (as determined by increase in MELD score > 5) up to Day 56 following administration of first dose of study drug.

Secondary:

- Determine the pharmacokinetics (PK) and pharmacodynamics (PD) of F-652 in patients with alcoholic hepatitis.

Additional:

- Assess the efficacy signal of F-652 in patients with alcoholic hepatitis as determined by:
 - a. Clinical: improvement in clinical status
 - b. Biochemical: Improvement in liver biochemistry, MELD and Lille scores at days 7, 28, 42 and 56
 - c. Biomarkers of IL 22 activity (CRP, SAA, triglycerides)

2.1 **Trial Design:**

The following study evaluations will be performed during the course of the Screening period (Day -3 to Day 0):

- Signed informed consent

CONFIDENTIAL

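### Section 7.1 makes no comparison with historical patients, although the Summary states the efficacy question that way, and it credits any 30% fall to the drug

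*Combined protocol and SAP*

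**What the plan says.** - **Study Summary, Objectives (c):** "Assess the efficacy signals of F-652 in patients with alcoholic hepatitis (compared to historical patient data) as determined by" clinical status, liver biochemistry, MELD and Lille scores, and biomarkers of IL-22 activity. Section 2 repeats the objective without the historical comparison.
- **Study Summary, Reference therapy:** "There is not a standard reference therapy or placebo against which the study product is being compared".
- **Section 1.9:** "With no treatment, approximately 15-20% of patients reach this outcome following study drug treatment". "We anticipate that a minimum of 50% will achieve this outcome". It plans 22 subjects for a two-sided superiority assessment of 50% against 20%. The main AST/ALT analysis is an exact 95% interval for the percentage of subjects with at least a 30% reduction.
- **Section 7.1, efficacy signal:** a 30% reduction in AST/ALT or triglycerides at Day 42 is taken to show that the drug works in that patient. The rate and its 95% interval are reported per dose level, with no reference rate. A random-intercept model of 30% change in AST, ALT then uses dose level and baseline characteristics "as the covariates to evaluate the change (efficacy) or drug by dose level".
- **Section 7.1, other endpoints:** "Linear mixed-effect models will be used to analyze the MELD score, triglycerides, CRP, and SAA1 in a similar way to the AST/ALT". Lille gets a paired t-test or signed-rank test.
- **Section 1.1:** "If alcohol use ceases, alcoholic hepatitis resolves slowly over weeks to months". The Schedule of Procedures confirms abstinence at every visit from Day 1, and steroids and pentoxifylline are allowed.

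**The concern.** The question in the Summary and the analyses in 7.1 do not meet. With every patient treated, the null hypothesis of a dose-level term is that the doses are equal. The Summary's null is that treated patients do no better than historical ones. For MELD and triglycerides nothing in 7.1 addresses the second null, and no reference value is given anywhere in the document.

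The patient-level rule has a related fault. The protocol expects improvement with abstinence, allows other active treatment and quotes an untreated response rate above zero. A 30% fall in one patient therefore cannot be assigned to F-652.

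Two misreadings are possible: natural recovery reported as a drug effect, and a flat dose term for MELD or triglycerides taken as absence of effect. Sections 1.6 and 2.4 use efficacy signals in decisions on further cohorts and the third dose, so the wording is not merely cosmetic.

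**Working it through.** **1. The plan's own figure.** Inputs from section 1.9: 20% reference, 50% anticipated, two-sided 5%, 80% power. A one-sample test against a fixed rate, with the variance taken at 50%, gives

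n = (1.960 + 0.842)² × 0.5 × 0.5 / 0.30² = 21.8, so 22.

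The stated 22 reproduces. A two-group comparison would need 39 per arm. The AST/ALT design therefore does contain an external benchmark of 20%.

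**2. What that benchmark can do at the planned 18.** The lower limit of the exact 95% interval exceeds 20% with at least 8 responders of 18 (8/18 gives 21.5% to 69.2%). The chance of 8 or more is 1.6% if the true rate is 20% and 76.0% if it is 50%.

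**3. What the dose term can do.** Pool the MELD strata to 6 patients per dose and let the true response be 50% at every dose. An exact 3×2 test of dose differences rejects in 2.8% of trials and an exact trend test in 3.9%, no more than the error rate. These stand in for the dose term of the models. The pooled interval in step 2 would detect the same drug in 76%.

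**4. Natural recovery under the patient-level rule.** Assume no drug effect and the 15-20% of section 1.9, read as an untreated rate. The chance of at least one credited patient is 1 − (1 − p)ⁿ:

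| n | p = 15% | p = 20% |
|---|---|---|
| 3 | 1 − 0.85³ = 39% | 1 − 0.80³ = 49% |
| 6 | 62% | 74% |
| 18 | 95% | 98% |

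**5. The composite.** Section 7.1 adds triglycerides as an alternative route to response. The documents give no background rate for that. If 10-30% of patients met it by chance, independently of AST/ALT (an assumption), the background would run from 1 − 0.85 × 0.90 = 24% to 1 − 0.80 × 0.70 = 44%. The 20% reference does not fit the composite.

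**6. When triglycerides are measured.** Section 5.2 and the lipid row of the Schedule of Procedures give Screening, Day 7, Day 14 if dosed, and Day 28. The analyte table below the schedule also lists the lipid profile under other chemistry, but the schedule gives it a row of its own, which I follow. Day 28 is then the last sample, and the last one common to all patients.

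**7. Illustration for MELD, of a test that 7.1 does not specify.** Assume a between-patient SD of 3 points for the 42-day change and a visit SD of 2. The SD of the observed change is √(9 + 4 + 4) = 4.12, and its standard error with 18 patients is 4.12/√18 = 0.97. With no drug effect and natural improvement of 1, 2 or 3 points, a t-test of change against zero rejects in about 16%, 49% and 83% of trials. None of these SDs or improvements is in the documents.

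**The case against.** The strongest reply concerns AST/ALT. A reader might infer that the plan has no external reference at all, and that a drug equally active at all doses would show no effect anywhere. The documents do not support that. Section 1.9 sets 50% against 20% with an exact interval over all subjects, and the per-dose rates and intervals in 7.1 are not tests of dose differences. What remains is that 7.1 does not repeat the benchmark, reports by dose level and changes the endpoint. The 15-20% also has no stated source, and its sentence refers both to no treatment and to study drug treatment.

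A reader might also infer that 7.1 tests change over time in MELD and the biomarkers. It lists no visit term and no test of change against zero for them; its paired test is for Lille alone. This reply stands, and it leaves dose level as the only treatment-related term.

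Third, CRP and SAA1 are named as markers of IL-22 activity, and section 1.5 reports dose-dependent CRP increases. A dose-level question is reasonable for them. This stands.

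Finally, these are additional objectives in a small uncontrolled study. No decision rule is attached to MELD, CRP or SAA1, the historical phrase appears only in the Summary, and the Summary leaves detail to a Statistical Analysis Plan. That limits the harm. It does not supply the missing comparison, and the conflict between the Summary and Section 2 still needs settling.

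**Conclusion.** The concern holds in a limited form. Section 7.1 makes no external comparison for any endpoint although the Summary poses one. For MELD, triglycerides, CRP and SAA1 its only listed treatment-related term cannot show an effect common to all doses. Its patient-level wording counts natural recovery as drug effect, with the chances shown in the table above; these rest on reading 15-20% as the untreated AST/ALT rate and on independent patients. The triglyceride route adds to that background by an unknown amount.

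It does not follow that AST/ALT efficacy is untestable, since section 1.9 gives the means. Nor does it follow that the plan will declare natural MELD improvement significant: the 16%, 49% and 83% only illustrate, under assumed SDs, what an added change-from-baseline test would do.

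**What to change.** In section 7.1:

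1. Replace the statement that a 30% fall shows the drug working in a patient with one that classes the patient as a responder.
2. Add the dose-pooled AST/ALT responder rate with its exact 95% interval, compared with the 20% reference in section 1.9. Do not apply that 20% to the composite with triglycerides.
3. State that the dose-level term answers only the dose-response question, which suits CRP and SAA1 as activity markers.
4. For MELD at Day 42 and triglycerides at Day 28, report the dose-pooled, baseline-adjusted mean change with a 95% interval. Then either compare it with a pre-specified historical mean change and its uncertainty, from patients in the same MELD range, or remove the historical comparison from the Summary objective for these endpoints and label the changes descriptive, not supporting an efficacy conclusion.

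This needs wording in the protocol and analysis plan and one pooled estimate per endpoint, with no added patients, visits or assays. The downside is that efficacy claims become weaker, and the sponsor must fix a historical reference in advance or give up the comparison.
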